8.4 TREATMENT OF OVERDOSE

The MTD of RO6889450 has been defined as	QD (based on tolerability
demonstrated when administered	[Phase I SAD study]
and the occurrence of only two dose limiting ev	vents [DLEs]
Phase I MAD study in healthy voluntee	rs). Any acci dental or intentional overd ose
or incorrect administration of study drug should	I be reported as an AE (see Appendix 2
for further details).	

For RO6889450, specific information regarding treatment of overdose is currently not available. In the event of any AE or overdose, appropriate supportive treatment should be initiated according to the participant's clinical signs and symptoms.

Decisions regarding dose interruptions or modifications will be made by the Investigator in consultation with the Medical Monitor based on the clinical evaluation of the participant.

In the event of an overdose, the Investigator should:

- 1. Contact the Medical Monitor immediately.
- 2. Closely monitor the participant for AE/SAE and laboratory abnormalities until resolved.
- Document the quantity of the excess dose, as well as the duration of the overdose, in the eCRF.

8.5 PHARMACOKINETICS

Blood samples for measurement of plasma concentrations of RO6889450 and derived metabolite(s) will be collected at the time points specified in Section 1.3. Plasma concentrations will be measured by a specific and validated LC-MS/MS method. Population PK analyses using nonlinear mixed effects modeling will be performed to analyze the sparse dose-plasma concentration-time data of RO6889450 and, if feasible, of the derived metabolite(s). The influence of covariates (e.g., weight and gender) on selected PK parameters (clearance and volume of distribution) will be investigated in an exploratory way. If deemed necessary, data may be pooled with data from other studies with RO6889450 (and derived metabolite[s] if available) in order to improve the parameter estimates of the model. The results of the analysis will be reported separately from the clinical study report (CSR).

Any volume of blood samples remaining after the specified analyses may also be used for additional assay development/validation experiments and for metabolite investigations.

The blood samples will be destroyed no later than two years after the date of the final CSR. Details on sampling procedures, sample storage, and shipment are given in the Sample Handling Manual.

Drug concentration information that may unblind the study will not be reported to investigative sites or blinded personnel until the study has been unblinded.

8.6 PHARMACODYNAMICS

Pharmacodynamic effects will not be assessed in this study.

8.7 FURTHER ASSESSMENTS

8.7.1 Mini International Neuropsychiatric Interview

The MINI (Sheehan et al 1998) is a brief, semi-structured diagnostic interview used to assess DSM-5 disorders and will be used to confirm the diagnosis of schizophrenia for

inclusion into this study. The MINI has been validated against the Structured Clinical Interview for DSM diagnoses. The interview with the participant will be conducted by a trained clinician or mental health professional. Administration time is approximately 20 minutes at screening visit only.

8.7.2 Wide Range Achievement Test 4

The Wide Range Achievement Test 4 (WRAT-4, Wilkinson et al 2006) measures basic reading skills. The test covers ages from 5 to 75 years old and takes approximately 15-30 minutes to administer. The WRAT-4-reading test (or an equivalent test in non-English speaking countries, if available) will be administered according to standard instructions, at screening only. The age-corrected standard score obtained will be used as pre-morbid IQ estimate. This assessment will not be performed in countries without validated translation. If validated translations become available, they may be used. Equivalent scales may be used, if available.

8.7.3 Wechsler Abbreviated Scale of Intelligence – Second Edition

The Wechsler Abbreviated Scale of Intelligence, Second Edition (WASI-II) is an intelligence test designed to estimate IQ in individuals aged 6 to 90 years (Wechsler 2011). The Full Scale Intelligence Quotient (FSIQ) score of the four-subtest form will be derived based on the total combined performance on the Vocabulary, Similarities, Block Design, and Matrix Reasoning subtests. A Verbal Comprehension Index (VCI) (Vocabulary and Similarities subtests) and a Perceptual Reasoning Index (Block Design, Matrix Reasoning subtests) will also be derived. The WASI-II four-subtest form should take approximately 30 minutes to administer. This assessment will not be performed in countries without validated translation. If validated translations become available, they may be used. Equivalent scales may be used, if available.

8.8 GENETICS

8.8.1 Clinical Genotyping

A mandatory whole blood sample will be taken for DNA extraction from every participant. If the sample is missed on baseline, it can be collected at any other scheduled visit. The DNA may be used for, but analysis is not limited to:

- Genetic variants of cytochrome P450s (e.g., CYP3A4, CYP3A5, CYP2C19), transporters (e.g., multidrug resistance protein 1 [MDR1]), receptors, or other proteins that might affect the metabolism, pharmacokinetics, pharmacodynamics, or safety of RO6889450.
- Genetic variants of the TAAR1 gene.
- Genetic variants of pathways related to schizophrenia and schizoaffective disorder, including but not limited to, genes related to disease and safety of RO6889450.
- Genes coding for human leukocyte antigens (i.e., human leukocyte antigen [HLA] gene family).

Data arising from all biosamples including samples for analyses of inherited DNA will be subject to the confidentiality standards described in Section 1.4 of Appendix 1. For participants who consent to research biosample repository (RBR), leftover samples will be transferred to RBR (see Section 8.9.1), otherwise the specimen will be destroyed after successful analysis.

The blood samples will be destroyed within two years after the date of the final CSR. Details on processes for collection and shipment of these samples can be found in Sample Handling Manual.

8.9 BIOMARKERS

8.9.1 Samples for Research Biosample Repository

8.9.1.1 Overview of the Research Biosample Repository

The Roche RBR is a centrally administered group of facilities for the long-term storage of human biologic specimens, including body fluids, solid tissues, and derivatives thereof (e.g., DNA, RNA, proteins, peptides). The collection, storage, and analysis of these specimens will facilitate the rational design of new pharmaceutical agents and the development of diagnostic tests, which may allow for individualized drug therapy for patients in the future.

Specimens will be collected from participants who give specific consent to participate in this optional RBR. Collected specimens will be used to achieve the following objectives:

- To study the association of biomarkers with efficacy, AEs, or progressive disease.
- To increase knowledge and understanding of disease biology.
- To study treatment response, including drug effects and the processes of drug absorption and disposition.
- To develop biomarker or diagnostic assays and establish the performance characteristics of these assays.

8.9.1.2 Sample Collection

Leftover blood samples will be stored in the RBR and for additional (assay) validation requirements or for other research purposes, including, but not limited to, research on biomarkers related to RO6889450 or schizophrenia.

For all samples, dates of consent and specimen collection should be recorded on the associated RBR page of the eCRF. For sampling procedures, storage conditions, and shipment instructions, see the separate Laboratory Manual.

RBR specimens will be stored and used until two years after the provision of the CSR. The RBR storage period will be in accordance with the IRB/EC-approved Informed Consent Form (ICF) and applicable laws (e.g., Health Authority requirements).

The repository specimens will be subject to the confidentiality standards (as described under Confidentiality and in Appendix 1).

8.10 MEDICAL RESOURCE UTILIZATION AND HEALTH ECONOMICS

Medical Resource Utilization and Health Economics parameters are not evaluated in this study.

8.11 TIMING OF STUDY ASSESSMENTS

8.11.1 Screening and Pretreatment Assessments

Written informed consent for participation in the study must be obtained before performing any study-specific screening tests or evaluations. Informed Consent Forms for enrolled participant and for participants who are not subsequently enrolled will be maintained at the study site.

All screening and pretreatment assessments must be completed and reviewed to confirm that participants meet all eligibility criteria. The Investigator will maintain a screening log to record details of all participants screened and to confirm eligibility or record reasons for screening failure.

Screening and pretreatment assessments will be performed within three to five weeks prior to start of study drug on Day 1. The screening period may be extended after discussion with the Sponsor (Medical Monitor/designee). During screening, the ECF will be completed and forwarded as soon as possible to the CTM or Monitor via the CRO ePIP for documentation and monitoring purposes. The Investigator will act as final decision maker regarding exclusion or inclusion of participants in the study.

In Part A of the study, all antipsychotics will be washed-out for at least one week prior to baseline/Day 1 (see Appendix 6 for details on atypical antipsychotic PK). Participants in Part A will have the option of inpatient or partial hospitalization for the washout period and for an additional week if they wish.

To enter the randomized, double-blind treatment period (Part A) there must be:

- No significant new or worsening psychiatric or medical illness since screening that in the opinion of the Investigator would interfere with the participant's ability to participate in the study.
- No change in medications since screening except as allowed in the concomitant medication section.

The treatment period begins with the investigational site call into IxRS confirming the participant's eligibility as per the confirmation of eligibility at baseline (see Section 5.3).

8.11.2 Assessments During Treatment

Under no circumstances will participants who enroll in this study and have completed treatment as specified, be permitted to be allocated a new randomization number and re-enroll in the study.

8.11.3 Assessments at Study Completion/Early Termination Visit

Participants who complete the study or discontinue from the study early are to return to the clinic for an end-of-treatment (EOT) visit with assessments as defined in the SoA (Section 1.3). They are then also to return for the required follow-up visits as described below.

8.11.4 Follow-Up Assessments

Follow-up phone calls will be made 7 and 14 days after the last dose of study drug or after early termination. An additional on-site follow-up visit will be performed 28 days after the last dose of study drug or after early termination.

After the study completion/early termination visit, AEs should be followed as outlined in Sections 8.3.1 and 8.3.3.

9. STATISTICAL CONSIDERATIONS

9.1 STATISTICAL HYPOTHESES

The primary efficacy analysis for this trial will compare each dose of RO6889450 with placebo at Week 12 for the primary endpoint. The following null (H_0) and alternative (H_1) hypotheses will be tested at a one-sided α =0.05 level:

- H₀: MEAN_{RO6889450} ≤ MEAN_{placebo} versus
- H1: MEANRO6889450 > MEANplacebo

for which the MEAN_{RO6889450} and MEAN_{placebo} refer to the mean change from baseline for RO6889450 and placebo, respectively. In Part B, doses will be tested sequentially, starting with the higher and followed by the lower dose arm to maintain Type I error at 5% one-sided.

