8.1.1.1 Brief Negative Symptom Scale

The BNSS (Strauss et al 2012) is a 13-item instrument designed for clinical trials that measures the severity of negative symptoms in five domains (subscales): blunted affect, alogia, asociality, anhedonia, and avolition/apathy. All ratings are based on a semi-structured interview with prompts and queries. Items are rated on a 7-point scale,

ranging from the symptom being absent (0) to severe (6). Subscale scores as well as a total score will be derived. The avolition/apathy subscore is the primary endpoint for this study. The full scale should take approximately 10-15 minutes to complete.

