9.2 SAMPLE SIZE DETERMINATION

Assuming a true effect size of 0.5, a number of 50 participants per arm will provide 80% power to see an effect with a one-sided type I error of 0.05. Thus, the goal is to have 50 evaluable participants per arm in Part A. Allowing for about 20% of the participants randomized not completing 12 weeks of treatment, approximately 125 participants will be randomized to Part A of the study.

In Part B, 50 participants per treatment arm will provide 80% power for an effect size of 0.5 and a one-sided type I error of 0.05. Allowing for about 25% of the participants randomized not completing 12 weeks of treatment, the goal is to have approximately 200 participants over all three dose groups, leading to 50 evaluable participants per treatment arm. In case of an unexpectedly high proportion of participants not completing 12 weeks of treatment (i.e. more than 25%), the number of randomized participants may be increased to achieve 150 patients completing 12 weeks of treatment.

These 200 participants will be recruited outside Japan. In addition to these 200 participants, approximately 20 participants will be recruited in Japan, leading to approximately additional 5 evaluable participants per treatment arm. The primary analysis will be based on all participants recruited outside Japan and in Japan and will be performed when all patients from outside Japan and in Japan complete the study.

Based on data from previously conducted studies in negative symptoms, the standard deviation for the change from baseline in the BNSS Avolition/Apathy Subscale (consisting of the sum of the two items 'Avolition/Apathy: Behavior' and 'Avolition/Apathy: Internal Experience') at Week 12 is about 2.8. Hence, an effect size of 0.5 translates to a reduction (versus placebo) of 1.4 points for the primary endpoint. With an anticipated sample size of 50 participants per arm, statistical significance at the one-sided type I error of 0.05, any observed reductions (versus placebo) by

approximately 0.92 or more points is expected to be statistically significant. For these calculations, the BNSS items are assumed to be rated on a 7-point (0–6) scale, with anchor points ranging from the symptom's being absent (0) to severe (6).

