#### **4.5.1 Primary Efficacy Endpoint**

##### **4.5.1.1 Definition of Primary Efficacy Endpoint**

The primary efficacy endpoint of the study is the change from baseline in the BNSS Avolition/Apathy subscore at Week 12.

The BNSS (Strauss et al 2012) is a 13-item instrument designed for clinical trials and other studies that measure the severity of negative symptoms in six domains (subscales), inclusive of one single-item domain of ‘Distress’ (see [Appendix 3](#)):

- **Blunted Affect** (three items): facial expression, vocal expression, expressive gestures;
- **Alogia** (two items): quantity of speech, spontaneous elaboration;

- **Asociality** (two items): asociality - behavior, asociality - internal experience;
- **Anhedonia** (three items): intensity of pleasure during activities, frequency of pleasure during activities, intensity of expected pleasure from future activities;
- **Avolition/Apathy** (two items): avolition - behavior, avolition - internal experience;
- **Distress** (single item): distress.

All ratings are based on a semi-structured interview with prompts and queries. Items are rated on a 7-point scale, ranging from the symptom being no impairment/normal (0), very slight deficit/questionable (1), mild deficit/mild (2), moderate deficit/moderate (3), moderately severe deficit/moderately severe (4), marked deficit/severe (5) to severe deficit/extremely severe (6). A total BNSS score is calculated by summing the 13 individual items so that the possible total score ranges from 0 to 78. Subscores are calculated by summing the individual items within each domain (subscale). The primary efficacy endpoint, the change in avolition/apathy subscale ranges from 0 to 12.

Higher scores indicate more negative symptoms. Hence negative values for change from baseline indicate improvement.

In study **Part A**, the BNSS is assessed by an approved remote centralized rater at Week -4, Day 1 (Baseline), Day 14, Day 28, Day 42, Day 56, Day 70, Day 84/EOT and Day 112 (FU). All assessments will be assigned to analysis study days according to the following table.

Assessment Days	Assigned Analysis Study Day
>88 or >4 days after last study medication	FU, will not be included in statistical analysis
78-88	84
64-77	70
50-63	56
36-49	42
22-35	28
2-21	14
-2-1	1
<-2	-35, will not be included in statistical analysis

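### Protocol Section 9.1 states the one-sided primary hypothesis in the wrong direction: as written, a dose succeeds only if its mean change is less favourable than placebo's

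*Protocol*

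**What the plan says.** Protocol Section 9.1 gives the null as "H₀: MEAN_{RO6889450} ≤ MEAN_{placebo} versus" and the alternative as "H1: MEANRO6889450 > MEANplacebo". The two means "refer to the mean change from baseline for RO6889450 and placebo, respectively", and the "hypotheses will be tested at a one-sided α =0.05 level". The same section orders the Part B doses, higher first and then lower, under this rule.

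The endpoint is the change from baseline at Week 12 in the BNSS avolition/apathy subscore. Protocol Section 8.1.1.1 scores each item from 0 (symptom absent) to 6 (severe). SAP Section 4.5.1.1 spells out the consequence for this endpoint: "Higher scores indicate more negative symptoms. Hence negative values for change from baseline indicate improvement".

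Protocol Section 9.2 points the other way from Section 9.1. It says "an effect size of 0.5 translates to a reduction (versus placebo) of 1.4 points for the primary endpoint", and it treats observed reductions of about 0.92 points or more as significant.

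Protocol Section 9.4.2 models change from baseline with no reversal of sign. It then refers the Week 12 comparison back to the hypothesis in Section 9.1.

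**The concern.** On this scale, a mean change on drug greater than on placebo is the less favourable result. That covers two cases: the drug arm deteriorates more, or both arms improve and the drug arm improves less. The alternative as written is therefore inferiority to placebo, while Section 9.2 plans for superiority.

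In a two-sided test this would be cosmetic. In a one-sided test the direction defines the rejection region. Followed literally, an effective dose could hardly ever succeed and an inferior one could. In Part B the sequential rule carries the error further, because the lower dose would be tested only after the higher dose had come out significantly less favourable than placebo. The optional Part B interim analyses, which assess the chance of final success, also depend on what counts as success.

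**Working it through.** **Inputs (Protocol Sections 9.1 and 9.2):** 50 evaluable participants per arm, equal allocation, SD of change 2.8, target difference 1.4 points (0.5 × 2.8), one-sided alpha 0.05. Write D for drug minus placebo in mean change from baseline, so benefit is D < 0.

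**Reproducing the plan's own figures, with benefit as a reduction**

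- Standard error of D: 2.8 × √(2/50) = 0.56.
- Standardised target: 1.4 / 0.56 = 2.5.
- Critical difference: 1.645 × 0.56 = 0.92 (normal). With t on 98 df the critical value is 1.661, giving 0.93.
- Power at D = −1.4, rejecting when D is below −0.92: Φ(2.5 − 1.645) = 0.804 (normal), or 0.799 (non-central t).

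These match the stated 50 per arm, 80% power and 0.92 points. Section 9.2 is therefore internally consistent, with rejection in the negative tail.

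**The rule as Section 9.1 writes it**

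The null is rejected when D exceeds +0.92.

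| True D (drug minus placebo) | P(reject), as written | P(reject), direction reversed |
|---|---|---|
| −1.4 (benefit) | 1 − Φ(1.645 + 2.5) ≈ 0.00002 | 0.80 |
| +1.4 (inferior to placebo) | Φ(2.5 − 1.645) ≈ 0.80 | ≈ 0.00002 |

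The non-central t calculation gives 1.8 × 10⁻⁵ for the small probability, against 1.7 × 10⁻⁵ from the normal.

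**With the Japanese participants included**

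Section 9.2 puts about 5 more evaluable participants per arm into the Part B primary analysis, so about 55 per arm.

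- Standard error: 2.8 × √(2/55) = 0.534.
- Power in the intended direction at D = −1.4: about 0.84.
- Probability of rejecting as written at D = −1.4: about 0.00001.

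**Is there a sign convention that rescues the wording?**

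None was found. Neither document defines change as baseline minus Week 12 or defines the means as improvement. The null and the alternative are reversed consistently with each other, so one symbol garbled in the PDF is an unlikely explanation.

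**The case against.** The best reply is that nobody would apply Section 9.1 literally. Section 9.2 follows it directly and gives a correctly directed significance boundary at the same alpha, so the contradiction has an obvious resolution. Section 9.4.2 also requires treatment differences with 90% confidence intervals at every visit, so the sign of the effect would be visible in the output. This stands as evidence of intent, and it makes an unnoticed false declaration unlikely. It does not repair the text: Section 9.4.2 names Section 9.1 as the hypothesis to be tested, and it reports the interval without saying which limit decides success.

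Three limits on reach also stand:

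- **Part A is unaffected in practice.** SAP Sections 4 and 4.5 plan descriptive summaries only, and Part A stopped with 27 participants randomised (SAP Section 1).
- **The Part B analysis plan is a separate document that was not available.** It may already state the right direction.
- **The Part B analysis would have about 55 per arm, not 50.** As shown above, this moves the figures only slightly.

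**Conclusion.** The concern holds. The formal primary hypothesis is reversed relative to the scale and to the protocol's own sample size section. Under the plan's assumptions (SD 2.8, 50 per arm, true difference of 1.4 points), literal application cuts the chance of success for an effective dose from about 0.80 to about 0.00002. It gives a dose inferior by the same amount an 0.80 chance of success.

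Those probabilities are conditional on Section 9.1 being executed as written; the intent is clear from Section 9.2. The practical effect falls on Part B. Sample size, alpha and the analysis model are not affected.

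It still must be corrected, because this is the prespecified rule for the primary test. Section 9.5 allows sponsor staff to see Part B results by treatment group at up to two interim analyses. Changing the tail of a one-sided test after that could look like a choice made on the data.

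**What to change.** In Protocol Section 9.1, for both parts, replace the two lines with:

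- H0: MEAN_RO6889450 ≥ MEAN_placebo
- H1: MEAN_RO6889450 < MEAN_placebo

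Add the success rule explicitly: the upper limit of the two-sided 90% confidence interval for RO6889450 minus placebo at Week 12 lies below 0. This is equivalent to the corrected one-sided 0.05 test and uses an interval that Section 9.4.2 already reports. Defining the means as improvement (baseline minus Week 12) would also work, but then the model and the reported differences would need the same convention.

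For Part A the change is for consistency only, and the Part A SAP needs no edit because it states no hypothesis. The Part B analysis plan should carry the same direction through the high-then-low dose sequence and any interim calculation of the chance of success. The correction should be dated before any unblinded look at Part B.

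The cost is two lines of wording plus one sentence, with no change to sample size, conduct or data collection.
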